7.1 Procedures for Site Selection

Investigational sites will be selected for this study based on high enrolment potential according to the protocol requirements and where a close working relationship with the nuclear medicine departments and electrophysiologists exists.

7.2 Inclusion Criteria

Patients may be included in the study if they meet all of the following criteria:

- (1) Patients ≥ 18 years of age at the time dated informed consent is obtained.
- (2) Female patients must be pre-menarchal, surgically sterile (had a documented bilateral oophorectomy and/or documented hysterectomy), postmenopausal (cessation of menses for more than 1 year), non-lactating, or, if of childbearing potential, a serum or urine pregnancy test with the results known prior to AdreView™ (Iobenguane I¹²³ Injection) administration is negative.
- (3) Patients willing and able to comply with all study procedures and a signed and dated informed consent is obtained before any study-procedure is carried out.
- (4) Heart failure NYHA class II or III for symptoms, patients with ischemic or non-ischemic heart disease, eligible for ICD implantation as per each site's standard of practice.
- (5) Non-ischemic dilated cardiomyopathy or ischemic heart disease of at least 3 months duration receiving guideline-directed optimal medical therapy.
- (6) $25\% \leq \text{LVEF} \leq 35\%$, performed within 3 months before or at time of enrolment, as measured by radionuclide ventriculography, or electrocardiogram [ECG]-gated SPECT myocardial perfusion imaging [MPI], or magnetic resonance imaging [MR], computed tomography [CT], or 3D or 2D echocardiography [Simpson's or multidisc method or equivalent only, M-mode echocardiography is not accepted].

In case LVEF measurement is performed within 3 months before enrolment, measurement should be performed at least 40 days after a hospitalisation for HF or acute coronary syndrome (including myocardial infarction), and to be valid, method of measurement should be in accordance with the protocol and the imaging exam should be made available to the Sponsor in digital format.

In case several valid LVEF measurements are available, the closest to enrolment will be used for inclusion determination.

- (7) Clinically stable HF in the medical judgment of the investigator (i.e., no significant changes in medication, no worsening of symptoms, no unscheduled visits to the doctor's office) for the past 30 days and no hospitalisation for HF or acute coronary syndrome (including myocardial infarction) in the past 40 days.
- (8) Reasonable expectation of meaningful survival for at least 1 year.

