
(1) Patients ≥ 18 years of age at the time dated informed consent is obtained.
 
(2) Female patients must be pre-menarchal, surgically sterile (had a documented bilateral oophorectomy and/or documented hysterectomy), postmenopausal (cessation of menses for more than 1 year), non-lactating, or, if of childbearing potential, a serum or urine pregnancy test with the results known prior to AdreView™ (Iobenguane I¹²³ Injection) administration) is negative.
 
(3) Patients willing and able to comply with all study procedures and a signed and dated informed consent is obtained before any study-procedure is carried out.
 
(4) Heart failure NYHA class II or III for symptoms, patients with ischemic or non-ischemic heart disease, eligible for ICD implantation as per each site's standard of practice.
 
(5) Non-ischemic dilated cardiomyopathy or ischemic heart disease of at least 3 months duration receiving guideline-directed optimal medical therapy.
 
(6) $25\% \leq \text{LVEF} \leq 35\%$, performed within 3 months before or at time of enrolment, as measured by radionuclide ventriculography, or electrocardiogram [ECG]-gated SPECT myocardial perfusion imaging [MPI], or magnetic resonance imaging [MR], computed tomography [CT], or 3D or 2D echocardiography [Simpson's or multidisc method or equivalent only, M-mode echocardiography is not accepted].
 
In case LVEF measurement is performed within 3 months before enrolment, measurement should be performed at least 40 days after a hospitalisation for HF or acute coronary syndrome (including myocardial infarction), and to be valid, method of measurement should be in accordance with the protocol and the imaging exam should be made available to the Sponsor in digital format.
 
In case several valid LVEF measurements are available, the closest to enrolment will be used for inclusion determination.
 
(7) Clinically stable HF in the medical judgment of the investigator (i.e., no significant changes in medication, no worsening of symptoms, no unscheduled visits to the doctor's office) for the past 30 days and no hospitalisation for HF or acute coronary syndrome (including myocardial infarction) in the past 40 days.
 
(8) Reasonable expectation of meaningful survival for at least 1 year.
		
Exclusion Criteria:		
Patients must be excluded from participating in this study if they meet any of the following criteria:		

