Planar imaging with AdreView™ is normally performed after intravenous administration of 370 MBq ($\pm 10\%$). Most $^{99\text{m}}\text{Tc}$ -labeled radiopharmaceuticals in common clinical use (with administered activities ranging from 370 to 1000 MBq) result in effective doses in the range of 2 to 6 mSv comparable to the doses received from other routinely performed diagnostic tests in radiology. The effective dose to an adult administered 370 MBq of AdreView™ is 4.8 mSv. The average background radiation dose per year in the United States is approximately 3 mSv and in Europe is approximately 2.4 mSv [[Biological Effects of Radiation 2003](#)] [[Ionising Radiation 1996](#)]. In recent procedure guidelines published by the European Association of Nuclear Medicine, the recommended dose of ^{123}I -mIBG for oncologic imaging studies in adults is 400 MBq [[Bombardieri et al. 2003](#)]. An administered ^{123}I -mIBG activity of 370 MBq has been demonstrated to allow consistently satisfactory planar and SPECT imaging with acceptable patient radiation dosimetry, which is particularly important for myocardial imaging studies in patients with heart disease, in whom the expected reduction in myocardial uptake may result in many uninterpretable SPECT studies if the lower dose historically employed for planar studies is used [[Carrio 2001](#)].

7

SELECTION AND WITHDRAWAL OF PATIENTS

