7.3 Exclusion Criteria

Patients must be excluded from participating in this study if they meet any of the following criteria:

- (1) Patients with existing ICD or patient having an indication of ICD implantation for secondary prevention of SCD.
- (2) Hospitalisation for HF or for acute coronary syndrome in the previous 40 days.
- (3) Patients where a cardiac resynchronisation therapy (CRT) is planned or indicated
- (4) Other indication for placement of device (sustained ventricular tachycardia, resuscitated sudden death, need for atrioventricular pacing).
- (5) NYHA class I or class IV symptoms at the time of study entry.
- (6) American College of Cardiology-American Heart Association (ACC-AHA) class III or class IV (unstable) angina.
- (7) Patient with chronic renal insufficiency defined as serum creatinine ≥ 3 mg/dl (or ≥ 265.2 μ mol/L).
- (8) Known or suspected hypersensitivity/allergy to Iobenguane or to any of the excipients in AdreView™ (Iobenguane I¹²³ Injection).
- (9) Patient who is pregnant or plans to become pregnant within 2 weeks after AdreView™ (Iobenguane I¹²³ Injection) administration.
- (10) Patient who has used any medication in the 2 weeks before AdreView™ (Iobenguane I¹²³ Injection) that could interfere with the test: e.g., but not limited to amitriptyline or derivatives, imipramine or derivatives, other antidepressants or drugs known or suspected to inhibit the norepinephrine transporter, antihypertensives that deplete norepinephrine stores or inhibit reuptake, sympathomimetic amines or cocaine.
- (11) Patients that have a medical condition that could interfere with the AdreView™ test (e.g., but not limited to left ventricular assist device, or prior heart transplant).
- (12) Patients who participated in a clinical study involving a drug or device within 30 days prior to study entry and patients participating in any other clinical study.
- (13) Patients having serious non-cardiac medical condition associated with significant elevation of plasma catecholamines, including pheochromocytoma.
- (14) Patients with a clinical diagnosis of (or being treated for) Parkinson's disease or Multiple System Atrophy.
- (15) The patient has participated in a research study using ionizing radiation in the previous 12 months.
- (16) Patients previously randomized in this study.

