8 TREATMENT OF PATIENTS

8.1 Investigational Medicinal Product (IMP)

8.1.1 AdreView™ (Iobenguane I¹²³ Injection)

After randomisation to either the AdreView™ group or the SoC group, all patients will receive at least one intravenous injection of 10 mCi (370 MBq) of AdreView™. A $\pm 10\%$ tolerance of the nominal dose will be allowed, thus yielding an acceptable dose range of 9 to 11 mCi (333 to 407 MBq) in accordance with the Package Insert/Summary of Product Characteristics/Investigator's Brochure (IB). AdreView™ will be administered in a volume of 5 mL (diluted using 0.9% sodium chloride as needed) and injected as a slow infusion over 1 to 2 minutes followed by 10 mL of saline flush injected over a maximum of 5 seconds. An administration volume of up to 15 mL may be used at sites where there are logistical limitations to achieving delivery of IMP within the timelines required to meet the $370 \pm 10\%$ MBq dose in a volume of 5 mL.

Patients being allocated to the AdreView™ low-risk group will receive a second injection of AdreView™ and planar /SPECT imaging 2 years (± 30 days) after the first one. If any of these patients voluntarily withdraw prior to completion of the study they will be offered this second AdreView™ scan prior to withdrawal being effective.

Refer to the Package Insert/Summary of Product Characteristics/IB and Appendix [15.2](#) for further detail.

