8.2 Method of Numbering Patients and Assigning Patients to Treatment Groups

A unique allocation number will be assigned to each patient in successive order of entering the study after signing the informed consent document at each centre. Patients who fail one or more inclusion/exclusion criteria may be re-screened at a later date and, if subsequently found to be eligible, randomized into the study. No patient may be randomized into the study more than once (i.e., patients withdrawn after randomization may not be re-screened). The allocation number will be unique for each patient in the study and will consist of 7 numbers in total: 3 numbers for the centre identification and 4 numbers for the patient identification at the centre (e.g., 0020001: first patient in centre No. 2). Please see the section on randomisation, Section [9.2](#).

Once an allocation number is assigned, it cannot be reassigned even if the patient is deemed ineligible or withdraws consent. To preserve the scientific integrity of the study, numbers must be assigned in numeric order.

Patients enrolled in the trial will be randomly assigned to the AdreView™ group (will receive AdreView™) or the SoC group (will receive AdreView™, however the results must remain blinded to the investigator). Allocation to the enrolment groups, including randomization, will be performed centrally (via an interactive web response system [IWRS]) by the Sponsor or contract research organisation (CRO).

No patient will be administered AdreView™ before it has been determined that the patient meets the study's inclusion/exclusion criteria and a signed and dated informed consent has been obtained.

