9.1 Screening/Enrolment Visit

Signed and dated informed consent must be obtained from all patients prior to any screening procedures. All patients must satisfy all the inclusion criteria and none of the exclusion criteria listed in Sections 7.2 and 7.3.

It is not necessary for all procedures to be performed during a single day.

At the screening/enrolment visit, LVEF function determination will be performed in cases where a previous LVEF measurement is not available. If there is a previous LVEF measurement performed within 3 months of enrolment, the investigator will check that this measurement was performed when the patient had no hospitalisations for HF or acute coronary syndrome, or if such hospitalisation happened then the LVEF measurement was performed 40 days after the event. Acceptable methods for LVEF determination are as follows: radionuclide ventriculography, ECG-gated SPECT MPI, MR, CT, or 3D or 2D echocardiography (Simpson's or multidisc method or equivalent only, M-mode echocardiography is not accepted). LVEF images will be sent to the sponsor in electronic format.

The following parameters will be collected:

- Demographics
- Medical history
- Concomitant medications, including guideline-directed optimal medical therapy. Should any patients not be receiving guideline-directed optimal medical therapy at target dose per local guidelines, the investigator must document the reason(s) why in the source documents.
- Vital signs (blood pressure, heart rate, respiratory rate, and pulse oximetry)
- Blood samples for serum chemistry and haematology and BNP or N-terminal pro b-type natriuretic peptide (NT proBNP) determination will be collected (according to [Table 2](#))
- Physical examination will be performed
- All female patients will undergo a serum or urine pregnancy test unless surgically sterile or post-menopausal
- A 12-lead ECG will be performed
- Collection of pre-inclusion events will commence

Waivers or protocol exceptions will not be granted prospectively by the Sponsor under any circumstances. Any exceptions to protocol-specified requirements will be considered as protocol deviations.

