15.2 AdreView™ (Iobenguane I¹²³ Injection)

AdreView™ must be ordered for each specific use date. It is recommended that this order be placed a minimum of 2 weekdays (Monday through Friday) before the scheduled visit date. Orders placed less than 2 weekdays before the scheduled visit must be approved by the Sponsor.

If AdreView™ is to be administered in the morning, the patient should abstain from eating or drinking (other than water) after midnight on the day of AdreView™ imaging. If AdreView™ is to be administered in the afternoon, the patient may have a light breakfast, after which the patient should abstain from eating or drinking (other than water). The patient should lie quietly for at least 15 minutes prior to administration of AdreView™. The first set of images will be obtained at 3 hours and 50 minutes post-injection and will be comprised of an anterior planar imaging of the chest performed according to the Imaging Manual provided by the Sponsor. This image will be followed by SPECT acquisition in accordance with said manual. While the planar imaging will be used for the primary and secondary efficacy analysis, the SPECT imaging will be used for exploratory analysis

For each imaging procedure, the patient will receive AdreView™ at rest, administered as an intravenous injection. The activity of AdreView™ should be measured in a dose calibrator within 1 hour prior to the scheduled administration time. The activity and time of measurement will be recorded on the eCRF. Aseptic conditions must be observed during handling of a patient dose. AdreView™ does not contain preservatives. The Sponsor or the designated CRO may request to review the quality control log book on the calibrators.

AdreView™ must be administered on the date for which the product is calibrated and no later than 6 hours post-calibration time. The preparation should be stored at 20 to 25°C (68 to 77°F); excursions permitted to 15 to 30°C (59 to 86°F). Storage should take place in accordance with national regulations for radioactive material.

The administration of radiopharmaceuticals creates risks to other persons, from external radiation or contamination from spills of urine, vomiting, etc. Waste must be disposed of according to national regulations for radioactive material.

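### Inclusion criterion 2 offers non-lactation as one alternative among several, so a lactating woman with a negative pregnancy test is eligible and nothing else in the protocol text stops her being dosed

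*Protocol*

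**What the plan says.** Section 7.2, criterion 2, lists five states for female patients: pre-menarchal, surgically sterile, and then "postmenopausal (cessation of menses for more than 1 year), non-lactating, or, if of childbearing potential, a serum or urine pregnancy test" with a negative result. The synopsis has the same structure: "non-lactating, or, if of childbearing potential, a serum or urine pregnancy test with the results known prior to" dosing.

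The only exclusion on reproductive status is number 9 in section 7.3, which begins "Patient who is pregnant or plans to become pregnant within 2 weeks after AdreView™" administration. It does not mention lactation.

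Section 8.2 makes dosing conditional on eligibility: "No patient will be administered AdreView™ before it has been determined that the patient meets" the inclusion and exclusion criteria. At screening (section 9.1), "All female patients will undergo a serum or urine pregnancy test unless surgically sterile or post-menopausal". Section 9.3 requires a further pregnancy test on the dosing day and allows the first dose only if it is negative. Section 9.5 requires a pregnancy test before the second scan at two years.

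**The concern.** A condition meant to apply to every woman has been placed inside a list of alternatives. There it excludes nobody who qualifies by another item.

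The person exposed would be a breast-fed infant. The protocol accepts in general terms that this type of product can affect people other than the patient. Section 15.2 says: "The administration of radiopharmaceuticals creates risks to other persons, from external radiation or contamination from spills of urine, vomiting, etc". That sentence does not name breast milk, so the link to an infant is an inference from the presence of the word non-lactating in the criterion. For the foetus, the protocol provides an exclusion, repeated tests and a reporting process (section 10.2.14). For a nursing infant it provides only this one word, which has no effect where it stands.

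The stake is participant and third-party safety and the accuracy of the eligibility text. No estimate, test or power figure depends on it.

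**Working it through.** No arithmetic applies. The check is of the logic of the sentence, followed by a search for any other rule that would close the gap.

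**Step 1: what kind of list is it?** The items cannot all be required together, since no woman is both pre-menarchal and postmenopausal. It is therefore a list of alternatives. If non-lactating is instead attached to the items before it, the final *or* still opens a separate route for a woman of childbearing potential with a negative test.

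**Step 2: evaluate it.** Label the items A1 pre-menarchal, A2 surgically sterile, A3 postmenopausal, A4 non-lactating, A5 of childbearing potential with a negative test. As written, the criterion is A1 or A2 or A3 or A4 or A5. The evident intent is A4 and (A1 or A2 or A3 or A5).

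| Woman of childbearing potential | A1–A3 | A4 | A5 | As written | As intended |
|---|---|---|---|---|---|
| Lactating, negative test | false | false | true | **met** | not met |
| Non-lactating, no test | false | true | false | **met** | not met |
| Non-lactating, negative test | false | true | true | met | met |

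The written form gives two unintended results, in the first two rows.

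**Step 3: does another rule close them?**

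- *Second row (no test):* closed. Exclusion 9 and the mandatory tests in sections 9.1 and 9.3 stop her. No criticism arises.
- *First row (lactating):* not closed.
  - Section 7.3: 0 of 16 exclusions name lactation, and she is not caught by number 9.
  - Sections 9.1, 9.3 and 9.5 and the schedule of events (Table 1): pregnancy tests only, which she passes.
  - Section 8.2: refers back to the same criteria, which she meets.
  - Sections 10.2.14 and 15.2: silent on lactation.
  - Section 7.4.1: the investigator may withdraw a patient, but this is discretionary and concerns the patient's own health.
  - SAP: adds no restriction.

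Lactation is mentioned twice in the supplied protocol text, both times in criterion 2 (synopsis and section 7.2).

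**Step 4: size.** The only dose figure is the patient's own, in section 6.4: "The effective dose to an adult administered 370 MBq of AdreView™ is 4.8 mSv". No infant dose can be derived from it, and the documents do not say how many participants might be lactating.

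**The case against.** The strongest reply is that no site would read the sentence this way. If every item is a free-standing alternative, non-lactating alone admits nearly all women and the other items do almost nothing. A sensible investigator would take it as a requirement. That is a fair account of likely practice, and it keeps the practical risk low. It does not rescue the text: even on the more generous grouping in step 1, the last item still admits her.

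A second reply is that section 8.1.1 sends sites elsewhere: "Refer to the Package Insert/Summary of Product Characteristics/IB". Those documents may bar lactating women, and consent must explain the hazards (section 13.2.2). This stands as a limit. Whether a lactating woman would actually be dosed cannot be judged from the documents supplied, so the conclusion is confined to the protocol wording.

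Third, few if any women are affected, and the SAP (sections 2.4 and 6) records that the sponsor ended the study early, so a change now protects few or no further participants. This too stands. It bears on priority, and it makes the main practical value of the correction the avoidance of re-use of the sentence.

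Finally, changing an entry criterion acts at entry, whereas low-risk patients in the AdreView group are dosed again at two years. That is a reasonable remark about the completeness of the remedy and is taken up in the fix.

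**Conclusion.** The point holds. As written, criterion 2 admits a lactating woman of childbearing potential with a negative pregnancy test, and no other rule in the protocol or SAP bars her. Of the two unintended results of the wording, one is closed elsewhere and this one is open.

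It is a minor drafting defect with a safety purpose. The number affected is unknown and probably very small or nil, the infant risk is not quantified in the documents, and no statistical result changes. The conclusion rests on the protocol text alone and assumes nothing about the content of the Package Insert, Summary of Product Characteristics or Investigator's Brochure.

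**What to change.** Take non-lactation out of the list, in both section 7.2 and the synopsis. For example: *A female patient must not be lactating. In addition, she must be pre-menarchal, surgically sterile or postmenopausal or, where she could conceive, have a negative pregnancy test (serum or urine) available before AdreView is given.* Adding lactation to exclusion criterion 9 would achieve the same.

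Two optional additions:

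- Ask about lactation before each dose, in sections 9.3 and 9.5. Table 1 schedules the eligibility check at screening only, so an entry criterion does not clearly cover the dose at two years.
- Carry the section 9.3 rule (test on the dosing day, dose only if negative) into section 9.5. A test before the second scan is already mandated, so this is for consistency only.

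The main change costs only the wording. The optional question adds a line to an existing visit. There is no new test or visit and no effect on sample size or analysis.

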The DSMB will act as an independent committee overseeing all safety aspects of the study, and is comprised of experts with relevant experience in, cardiology, clinical trials safety, biostatistics and epidemiology. The DSMB members are independent of investigators entering or caring for patients in the study, are independent of the other study committees and are not involved in any other of the study activities than their role in the DSMB. The DSMB may recommend to the ESC and Sponsor termination of the study at any time should prospective ethical or safety guidelines not be met, or propose protocol amendments to ensure safety of study individuals. In addition, based on the regular or interim analyses performed, the DSMB may recommend to the ESC and Sponsor to re-calculate the sample size, or prolong or terminate the study should the power of the study become non-sufficient to achieve its objectives.

This study will be conducted at approximately 130 centres in the USA, Canada and Europe. At least 2354 patients will be screened (taking into account approximately 15% screen failure rate) in order to include at least 2001 patients.

It is anticipated that patients will participate in the study until sufficient endpoints have been accrued which may correspond to an average of 2.75 to 3 years individual follow-up. The total study duration is expected to be approximately 6 years and the total required number of primary endpoint events observed is 247.

Only patients with stable heart failure who have been under guideline-directed optimal medical therapy for at least 3 months and have $25\% \leq \text{LVEF} \leq 35\%$ will be considered for inclusion. Patients with $\text{LVEF} > 35\%$ will be excluded. Patients must have $25\% \leq \text{LVEF} \leq 35\%$ as measured in the previous 3 months before enrolment with no hospitalisations for HF or acute coronary syndrome during this period of time. In case these patients have a hospitalisation for HF or acute coronary syndrome, the LVEF measurement will only be valid if performed 40 days after this event. Patients without a LVEF measurement will have the test performed at screening. All LVEF images will be sent to the Sponsor. Study procedures will be performed as detailed in Section 9.

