6.4 Risks and Benefits to Patients

The study rationale and justification have been detailed in Section 4 above.

Current HF guidelines recommend implantation of ICD for primary prevention of SCD to reduce total mortality in NYHA class II and III patients with a LVEF $\leq 35\%$ after a minimum of 3 months of guideline-directed optimal medical therapy [Yancy et al. 2013]. However, there are still doubts about using the LVEF as the main criteria to decide on ICD implantation. [Al-Khatib et al. 2014] have suggested that perhaps devices for primary prevention of SCD should only be implanted in patients with LVEF $< 30\%$, thus identifying a population of patients with $30\% \leq \text{LVEF} \leq 35\%$ that might not benefit from ICD implantation. More recently Køber et al found that prophylactic ICD implantation was not associated with a significantly lower long-term rate of death from any cause than was usual clinical care in patients with non-ischemic HF and LVEF $\leq 35\%$ [Køber et al. 2016]. Furthermore, a pooled analysis of 1054 patients with class III HF included in SCD-HeFT, MADIT-II and DEFINITE trials, showed no significant survival benefit of ICD versus medical therapy [Barra et al. 2016]; while an ICD will prevent about 2 deaths per year for every 100 devices in patients with mild HF (NYHA class II) [Ponikowski et al. 2016]. Thus, it is expected that better risk stratification will lead to better patient selection improving the risk/benefit of ICD implantation.

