The study will recruit patients with stable HF who have been under guideline-directed medical therapy for at least 3 months and have $25\% \leq \text{LVEF} \leq 35\%$. Patients will be randomised to one of the 2 following groups. In one group, AdreView™ imaging will lead the decision of whether or not to implant an ICD and in the other it will not (the AdreView™ scan result will not be disclosed to the investigator). AdreView™ is a diagnostic radiopharmaceutical approved in the USA and several European countries for the identification of HF patients, NYHA class II and III with lower 1- and 2-year mortality risk. Patients randomised to the AdreView™ arm will have an ICD implanted within 45 days of randomisation if they are deemed to be at high risk according to the definition in Section 6.1 (AdreView™ H/M ratio [measured on an anterior planar image obtained at 3 hours and 50 minutes post-injection and calculated according to the instructions in the Imaging Manual] lower than 1.6). These patients should then face the same risks and benefits as those managed according to guidelines in the regular clinical setting.

Patients considered to be at low risk by AdreView™ imaging (i.e., those with a planar image H/M ratio ≥ 1.6) will not receive an ICD, thus avoiding the exposure to complications; however they may face the risk that a potentially beneficial ICD implantation is withheld. GE Healthcare-sponsored study reports used for regulatory submissions (MBG311, MBG312 and MBG313; reports available upon request) have consistently showed a significant difference in all-cause and cardiac mortality between the high and the low risk groups in favour of the latter. These patients will also continue to receive the usual guideline-directed optimal medical therapy needed for their condition, including all the necessary follow-up visits and tests deemed necessary by the physician in charge. In addition, these patients will undergo a second AdreView™ H/M ratio determination 2 years after the first one in order to assess if their risk level has increased and ICD implantation is warranted. Moreover and as described in the protocol, the DSMB will regularly assess all safety aspects of the study.

Patients randomised to the SoC group will be treated in accordance to guidelines including having an ICD implanted, and therefore should then face the same risks and benefits as those managed according to guidelines in the regular clinical setting.

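### Inclusion criterion 7.2(5) does not carry the 3 months of optimal medical therapy that Sections 6.1 and 6.4 require, and 7.2(6) does not tie the qualifying LVEF to that therapy

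*Protocol*

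**What the plan says.** Three places in the protocol put a duration on therapy.

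- Section 6.1 (and the synopsis) considers for inclusion "Only patients with stable heart failure who have been under guideline-directed optimal medical therapy for at least 3 months" with LVEF between 25% and 35%.
- Section 6.4 describes the recruited population as "stable HF who have been under guideline-directed medical therapy for at least 3 months".
- Section 6.4 also gives the guideline basis: an ICD is recommended at LVEF of 35% or less "after a minimum of 3 months of guideline-directed optimal medical therapy".

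Section 9.1 requires patients to satisfy the lists in Sections 7.2 and 7.3. The relevant criteria in 7.2 are:

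- (4): the patient is eligible for an ICD under the site's own practice.
- (5): "Non-ischemic dilated cardiomyopathy or ischemic heart disease of at least 3 months duration receiving guideline-directed optimal medical therapy".
- (6): LVEF of 25% to 35%, "performed within 3 months before or at time of enrolment". For an earlier value, the "measurement should be performed at least 40 days after a hospitalisation for HF or acute coronary syndrome". If several valid values exist, the one nearest enrolment counts.
- (7): 30 days without significant medication change.

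Section 9.1 has LVEF measured at screening only where no previous value exists.

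**The concern.** The list that a site checks is weaker than the population the protocol describes. Take a patient with long-standing ischaemic disease who reached optimal therapy 5 weeks ago. That patient meets (5), (6) and (7) as written but falls outside 6.1. Take another who began therapy 90 days ago and whose only LVEF was taken that day. That patient satisfies 6.1 as well, yet the LVEF says nothing about response to therapy.

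The primary objective concerns ICD decisions in patients whose LVEF is 25% to 35%, in a trial whose own rationale places that decision after 3 months of therapy. Patients whose LVEF has since risen above 35% would blur the comparison.

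The analysis set is also affected. SAP 4.1.1 builds the safety set from patients who met every inclusion criterion, and SAP 4.1.2 draws the full analysis set from it. How (5) is read can therefore change who enters the primary analysis. Protocol 12.2 instead analyses everyone randomised, and 12.2.1 gives protocol violations no role.

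**Working it through.** **1. How criterion (5) reads.** The duration phrase directly follows the two heart diseases, and therapy is then mentioned with no duration. The amendment history in Section 16.2 supports this reading. Before Amendment A02 the criterion ended at the disease duration. A02 gave the 3-month therapy rule as a reason for the change, but added to (5) only that therapy is being received. The stated intent did not reach the operative criterion.

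**2. Date arithmetic** (enrolment = day 0, 3 months taken as 90 days).

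| Rule applied | Latest start of therapy | Oldest LVEF | Worst case |
|---|---|---|---|
| 7.2 only | day -30, from (7) | day -90, from (6) | LVEF 90 - 30 = 60 days before therapy |
| 7.2 and 6.1 | day -90 | day -90 | LVEF on the day therapy starts |

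For a day -90 LVEF to reflect 90 days of therapy, therapy would have to start by day -180. Nothing in the documents requires that.

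**3. The plan's own figures** (Protocol 12.8: one-sided alpha 0.025, power 80%, 1:1 allocation, margin 1.20, assumed HR 0.84).

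Events = 4 × (1.960 + 0.842)² / [ln(0.84/1.20)]² = 246.8, so 247. This reproduces the plan.

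For N, I assume exponential survival, uniform accrual over 18 months and 48 months in total. A 36-month survival of 0.887 gives λ = -ln(0.887)/36 = 0.00333 per month. The event probability is 1 - (e^(-30λ) - e^(-48λ))/(18λ) = 0.1217. With both arms at that rate, N = 247/0.1217 = 2030, close to 2001. With the SoC hazard at λ/0.84, the mean probability is 0.1324 and N = 1866, about 7% below 2001. Neither figure depends on the present point.

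**4. What dilution would do.** The documents give no recovery rate, so everything in this step is illustration. Let a share f of patients have recovered LVEF, with HR 1 between arms and r times the SoC hazard. Approximately:

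HR(mixed) = [(1 - f)·HR + f·r] / [(1 - f) + f·r]

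Probability of showing non-inferiority = Φ( ln(1.20/HR(mixed)) × √247/2 - 1.960 )

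For the share, suppose 20% to 40% qualify on an LVEF taken before 3 months of therapy and 10% to 30% of those have recovered. Then f runs from 0.20 × 0.10 = 2% to 0.40 × 0.30 = 12%, or 40 to 240 of 2001. With r = 1, the strongest dilution considered:

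| True HR in intended population | f | HR(mixed) | Chance of showing non-inferiority |
|---|---|---|---|
| 0.84 | 0% | 0.840 | 80% |
| 0.84 | 2% | 0.843 | 79% |
| 0.84 | 12% | 0.859 | 75% |
| 1.20 | 0% | 1.200 | 2.5% |
| 1.20 | 2% | 1.196 | 2.7% |
| 1.20 | 12% | 1.176 | 3.6% |

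At a true HR of exactly 1, dilution changes nothing.

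A wider grid (f from 5% to 30%, r from 0.25 to 1.0), computed from 48-month event probabilities at a true HR of 0.84, gives mixed HRs of 0.843 to 0.888. Power at 247 events is 79% to 66%, and 252 to 346 events are needed for 80%. Expected deaths by 48 months with 2001 patients are 208 to 271, against 265 with no recovered patients.

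**The case against.** The strongest reply is that the protocol does contain the rule. Section 6.1 states it as a condition for inclusion, 6.4 repeats it, and (5) is loose enough that a reader could attach the 3 months to therapy. This stands in part: the intention is not missing. What is missing is a clear statement of it in the list that 9.1 makes decisive.

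There are also safeguards. A site following the guideline in 6.4 could fail the 5-week patient on criterion (4), and a newer valid LVEF above 35% would exclude a patient under (6). Both are partial. Criterion (4) varies with site practice, and the nearest-value rule works only if a second measurement exists, which 9.1 does not require.

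Some stronger inferences are not supported:

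- **That the qualifying LVEF can predate therapy on any reading.** With 6.1 applied it cannot; the worst case is the day therapy starts.
- **That the loose criteria bias the trial towards non-inferiority.** They apply equally to both arms, and at the planned HR of 0.84 dilution makes non-inferiority harder to show.
- **That SoC patients will be implanted on an outdated value.** Table 1, note h, ties SoC implantation to each site's standard of care, so implantation does not follow automatically.
- **That 6.1 already requires an LVEF taken after 3 months of therapy.** Its LVEF window is the same 3 months, with no link to therapy.

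**Conclusion.** The mismatch between 6.1/6.4 and 7.2(5) is established from the text, as is the absence of any link between LVEF date and therapy in 7.2(6) and 9.1. It can change who is enrolled and, through SAP 4.1.1 and 4.1.2, who enters the full analysis set.

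Its numerical size cannot be derived from the documents. The 40 to 240 patients above are the product of two assumed ranges and should not be read as an estimate. Under those shares the effects are modest: up to about 5 points of power at HR 0.84, and up to about 1 point of one-sided error at HR 1.20. They rest on HR 1 among recovered patients and a hazard no higher than SoC, neither of which the documents state. A reader might infer that 247 events or 2001 patients is wrong; nothing here shows that. The point merits correction, but it does not undermine the design.

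**What to change.** 1. Reconcile 7.2(5) with 6.1 and 6.4, so that the protocol's own 3-month therapy requirement appears in the criterion that sites apply.
2. Reconcile 7.2(6) and 9.1 with the guideline statement in 6.4 on when the qualifying LVEF is measured relative to therapy. The sponsor should state that rule explicitly; 6.1 does not settle it.
3. Flag randomised patients with less than 3 months of therapy at enrolment, or with an LVEF dated before that period was complete. Define before database lock which date counts as the start of therapy. Repeat the primary Cox analysis without flagged patients as a sensitivity analysis. The flag uses only pre-randomisation dates, so the arms remain comparable within the subset.
4. Keep all randomised patients as the primary population, as Protocol 12.2 has it, and align SAP 4.1.1 and 4.1.2 with that.

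The cost is amendment wording, two dates and one extra analysis. Part of the data probably exists: SAP 5.1.3 relies on medication start and end dates, and LVEF images go to the sponsor. The downside for enrolment is that some patients would need the screening LVEF or would enter a few weeks later. SAP 2.4 and Section 6 report that the sponsor ended the study early, so items 3 and 4 are what can still be acted on. The wording changes matter only if enrolment resumes or the protocol is reused.
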